#### 8.4 SAFETY MEASUREMENTS

The following safety evaluations will be performed at Screening and during the Treatment Phase of the study:

- Medical history to capture underlying conditions
- Physical examinations
- Evaluation of AEs at post-screening visits
- ECOG/WHO performance status
- Vital signs and weight
- Laboratory tests: haematology, clinical chemistry, urinalysis (Screening only), pregnancy test (at screening and during study when clinically indicated), thyroid function, hepatitis B/C testing (Screening only).
- Concomitant medications/procedures (prior medications at screening)
- Injection site reactions

# 8.4.1 Medical History

The Investigator or qualified designee will obtain the patient's medical history at the Screening visit. Medical history will include all active conditions, and any conditions diagnosed within the preceding 5 years that are considered to be clinically significant by the Investigator.

# 8.4.2 Physical Examination

A full physical examination, including assessment of injections received prior to Screening, and pre-existing injection site reactions (i.e. BCG or prior cancer treatment reactions), will be performed at Screening, at every visit where IMM-101 is administered and at the EOS visit.

Additional physical examinations to those scheduled will be performed as per the Investigator's routine procedures.

# **8.4.3** Adverse Events

All AEs will be recorded on the patient's eCRF from the time of informed consent. All AEs will be followed until resolution, death, or 30 days after the last administration of study treatment (whichever comes first). See section 9.2 for further information on the recording of AEs.

#### 8.4.4 ECOG/WHO Performance Status Assessment

To be eligible for entry into this study, patients must have an ECOG/WHO Performance Status of  $\leq 1$  at Week 0, Visit 1. Two observers are required to assess performance status at the Screening and Week 0, Visit 1 assessments. If there is any discrepancy between the two scores, the highest (worst) assessment will be used. Subsequent assessments are at Week 4 and every 4 weeks thereafter on study and only require one assessor. The assessment guidelines are provided in Appendix  $2^{[24]}$ .

#### 8.4.5 Vital Signs and Weight

Vitals signs (resting blood pressure, pulse, and body temperature) and weight will be measured and recorded in the patient's eCRF at Screening, at every visit where IMM-101 is administered and at the EOS visit.

Patients will be followed by vital sign monitoring for at least 2 hours after administration of the first dose of IMM-101 with monitoring every 15 minutes during this period, under medical supervision with resuscitation facilities available as a precautionary measure.

Page 55 of 98

Additional measures of vital signs to those scheduled in this study will be performed as per the Investigator's routine procedures.

# 8.4.6 Electrocardiogram

12-lead ECG measures will be recorded at Screening and at the EOS visit. Additional 12-lead ECG measures to those scheduled in this study may be performed as per the Investigator's routine procedures. The results will be reviewed by the Investigator and recorded in the patient's eCRF as normal, abnormal but not clinically significant, or abnormal and clinically significant. A description should be given for any clinically significant abnormality. The QT interval corrected using Fridericia's factor will be recorded.

# 8.4.7 Laboratory Evaluation

Laboratory safety tests (e.g., complete blood count (CBC), clinical chemistries, and thyroid function), will be assessed at designated intervals throughout the study according to Table 1 (see also Appendix 1).

**Table 1: Study Timelines for Laboratory Samples** 

Timeline	Measure	Volume 		
Screening (Day -21 to -1)	Serum pregnancy test. Hepatitis B/C test  Safety blood analysis: CBC with differential, clinical chemistry including ALT, ALP, AST, bilirubin (total, direct), albumin, lipase, amylase, GGT, LDH, urea, electrolytes, creatinine, urea, glucose, TSH, free T4, free T3 Urinalysis	10 mL blood		
Treatment Phase 	Serum pregnancy test (as required)			
Visit 1 (Week 0) 				
Visit 2 (Week 2)	Safety blood analysis:			
Visit 2 (Week 2) Visit 3 (Week 4)	CBC with differential, clinical chemistry including ALT,			
Visit 5 (Week 8)	ALP, AST, bilirubin (total, direct), albumin, lipase, amylase,			
Visit 6 (Week 10)	GGT, LDH, urea, electrolytes, creatinine, urea, glucose, TSH,			
Visit 7 (Week 12)	free T4, free T3			
Visit 9 (Week 16)				
Visit 11 (Week 20)				
Visit 13 (Week 24)				
Visit 15 (Week 28)				
Visit 17 (Week 32)				
Visit 19 (Week 36)				
Visit 21 (Week 40)				
Visit 23 (Week 44)				
Visit 25 (Week 48)				
Visit 27 (Week 52)				
Visit 29 (Week 56)				
Visit 31 (Week 60)				
Visit 33 (Week 64) Visit 35 (Week 68)				
Visit 37 (Week 72)				
Visit 39 (Week 76)				
1 1511 57 (11 CCR /U)				
Withdrawal/EOS Visit	Safety blood analysis: CBC with differential, clinical chemistry including ALT, ALP, AST, bilirubin (total, direct), albumin, lipase, amylase, GGT, LDH, urea, electrolytes, creatinine, urea, glucose, TSH, free T4, free T3	10 mL blood		

ALP: alkaline phosphatase; ALT: alanine transaminase; AST: aspartate transaminase; CBC: complete blood count; GGT: gamma-glutamyl transferase; LDH: lactate dehydrogenase.

# 8.4.8 Pregnancy Test

A serum pregnancy test ( $\beta$ -hCG) will be conducted for all eligible females of child-bearing potential during Screening and at any other time during the study if pregnancy is suspected (Study Schedule of Assessments, in Appendix 1). Female patients with reproductive potential must have a negative serum pregnancy test ( $\beta$ -hCG) documented within 72 hours prior to the first dose of study drug.

The maximum volume of blood collected per patient at a single visit specifically for the safety endpoints will not exceed 10 mL Blood samples for immunomarker analyses are provided in Section 9.6

<sup>2 Only to be repeated if more than 7 days between screening test and commencing any study treatment (Visit 1)

<sup>3 Blood samples may be taken one day before the day of dosing (visit day).

Page 57 of 98

See section 6.6 for contraception requirements on study and handling of pregnancy.

#### **8.4.9** Concomitant Medications

See section 6.5 for information on prohibited and allowed concomitant medications.

# **8.4.10** Injection Site Reactions

Mild or moderate local reactions at the injection site are expected. Patients are likely to experience a skin reaction and some discomfort around the injection site. Each patient will be given advice regarding the management of local injection site reactions and generalised systemic symptoms (e.g., pyrexia). Where symptoms persist or result in functional limitations, patients will be advised to attend the next possible research clinic or see their own GP.

Before each administration of IMM-101, previous injection sites must be inspected for local reaction(s). Although a formal assessment is performed before each injection, an injection site reaction may be recorded as an AE at any time if considered appropriate to do so by the Investigator.

During the study, at the discretion of the Investigator, the dose interval may be modified provided the minimum period between doses is at least 12 days (14±2 days) between visits 1-2, 2-3, 5-6 and 6-7. The 28 day interval ±2 days between other doses (3-5, 7-9 and all after this point) should be maintained, subject to skin reactions or other immune-related AEs as detailed below.

Local skin reactions are expected but in the event of an injection site reaction of ≥Grade 3 (severe) as measured by the NCI CTCAE v4.03, at the discretion of the Investigator, patients may be administered a half dose of IMM-101 (i.e., a single 0.05 mL intradermal injection of IMM-101) or the dosing interval may be increased or both. If the dosing interval is increased, the patient should attend the study site for safety assessments at least every 4 weeks.

If dosing is discontinued or the patient withdraws from the study as a result of an intolerable injection site reaction, this must be recorded in the eCRF.

#### 8.5 EFFICACY MEASUREMENTS

The primary efficacy endpoint of the study is ORR. Response assessment based on RECIST 1.1 is used as the primary assessment of ORR and ORR based on irRC will be evaluated as a secondary assessment of the efficacy endpoints.

#### 8.5.1 Tumour Burden

During the study, response will be assessed by CT or MRI, the same imaging method used at baseline (Screening) and during the remainder of the study for each patient. The preferred method is contrast enhanced CT of the chest, abdomen and pelvis. A baseline MRI of the brain should be done for patients with a history or clinical symptoms of brain metastases. MRI can be used as an alternative method to CT scan if the patient has a clinical contraindication for iodine-based IV contrast or to better assess the disease. CT head scan can be used as an alternative to MRI of the brain if IV gadolinium is contraindicated.

All baseline evaluations must be performed no more than 21 days before enrolment and should be as close as possible to the beginning of treatment. All known and suspected sites of disease should be assessed and at least one measurable lesion according to RECIST 1.1 criteria must be present at screening. A maximum of 5 target lesions can be recorded with a maximum of 2 lesions per organ representative of all involved organs (see Section 8.5.2.1). All measurements should be recorded in millimetres (mm). Imaging based evaluation should **always** be used

Page 58 of 98

rather than clinical examination unless the lesion(s) being followed cannot be imaged but are assessable by clinical exam.

All scans will be reviewed by experienced radiographers trained in the study requirements. The scans will be read in sequence, and each review should be within 4 weeks of the scan being conducted to ensure that a confirmatory scan can be conducted as required.

Baseline scans will be assessed (and non-target/target lesions identified from the baseline scan alone) prior to the review of post baseline scans.

Where possible, the same radiographer should review the scan for both RECIST 1.1 and irRC at the same time, and review all scans for the same patient.

Further details are provided in the IMM-101-015 Study Operations Manual.

Chest CT is preferred over chest x-ray, however lesions on chest x-ray may be considered measurable if they are clearly defined and surrounded by aerated lung.

Clinical lesions will only be considered measurable when they are superficial and  $\geq 10$  mm diameter by caliper measurement. For the case of skin lesions, documentation by colour photography using a ruler to estimate the size of the lesion is possible, but CT is always preferred.

Ultrasound should not be used for lesion measurement. If new lesions are identified by ultrasound in the course of the study, confirmation by CT or MRI should take place.

Endoscopy and laparoscopy should not be used for objective tumour evaluation.

Immune Related Response Criteria (irRC) is also used in this study for assessment of response and may be used for the purposes of managing patients on protocol treatment and decision making for discontinuation of study therapy due to disease progression. For the purposes of irRC, up to five lesions in a single organ may be recorded with a maximum of 10 visceral and five cutaneous index lesions (see Section 8.5.2.3). The first post-baseline radiological assessment of tumour response status will be performed at Week 12 (±7 days) for patients in cohort A and at Week 6 (±7 days) for patients in cohort B unless there is clinical indication (based on Investigator's assessment) warranting earlier imaging. Subsequent radiological assessments are at 8 weekly intervals thereafter on study. Beyond week 52, scans may be conducted every 12 weeks at the discretion of the investigator.

If imaging shows a complete response (CR) or partial response (PR), according to the rules in 8.5.3.1, tumour imaging should be repeated at least 4 weeks later to confirm response, per RECIST 1.1 recommendations. The results of both the first (original) scan showing a CR or PR according to the rules in 8.5.3.1 as well as those of the confirmatory scan should be entered into the eCRF. The values for the original scan should not be amended in the eCRF even if the confirmatory scan does not confirm the results of the original scan. The confirmed response is used for the calculation of BOR (and hence the primary endpoint of ORR). However, BOR and hence ORR, using unconfirmed responses will also be calculated for comparability with published data. Following a confirmatory scan, the patient will then return to regular scheduled imaging every 8 weeks relative to the Week 12 scan (Cohort A) or Week 6 scan (Cohort B) and 12 weekly for patients still on study after Week 52. Patients who obtain a confirmation scan do not need to undergo scheduled imaging assessment 4 weeks later (e.g., if a patient obtains a scan at Week 16 to confirm a Week 12 response, their next scheduled scan would not be performed until Week 28, with no scan at Week 20). Once a response is confirmed, repeat scans are not required to confirm subsequent instances of the same response.

Page 59 of 98

If imaging shows PD, it is at the discretion of the investigator whether to continue or stop study treatment (i.e. both IMM-101 and nivolumab/ipilimumab) recognising that some patients with advanced melanoma can have a transient tumour flare in the first few months after start of immunotherapy with subsequent disease response. This decision will be based on clinical judgment but to continue treatment on study after disease progression is identified by a scan, the patient should have:

- Absence of clinical symptoms and signs indicating disease progression (including worsening of laboratory values)
- No decline in performance status
- Absence of disease symptoms indicative of requiring alternative treatment
- No clinically relevant adverse effects related to study treatment

Patients in cohort B who fail to respond to treatment with IMM-101 + nivolumab i.e., they have either documented progression by RECIST 1.1, or clinical progression (but without meeting the RECIST 1.1 rules for progressive disease), and, in both cases have no prior recorded response, have the option to change treatment on study to ipilimumab + IMM-101 if the investigator considers this in the patient's best interest and the patient has not previously received ipilimumab off study (monotherapy or in combination). Any patients who discontinue study treatment for reasons other than progression and for whom no further treatment is deemed appropriate or desired, should remain on study and have scheduled scans until documented progression.

At baseline, tumour lesions/lymph nodes will be categorised as measurable or non-measurable as follows:

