If imaging shows a complete response (CR) or partial response (PR), tumour imaging should be repeated at least 4 weeks later to confirm response, per RECIST 1.1 recommendations. Once a response is confirmed, repeat scans are not required to confirm subsequent instances of the same response. Patients will then return to regular scheduled imaging every 8 weeks relative to the Week 12 scan (Cohort A) or Week 6 scan (Cohort B) and 12 weekly for patients still on study after Week 52. Patients who obtain a confirmation scan do not need to undergo scheduled imaging assessment 4 weeks later (e.g., if a patient obtains a scan at Week 16 to confirm a Week 12 response, their next scheduled scan would not be performed until Week 28, with no scan at Week 20).

If imaging shows PD, it is at the discretion of the Investigator whether to keep a patient on study treatment or to stop study treatment until imaging is repeated approximately 4 weeks later in order to confirm PD, per irRC recommendations.

Confirmatory scans for responses by irRC may be carried out at the discretion of the Investigator to assist in managing treatment on study.

For all scans, assessments per RECIST 1.1 and irRC will be recorded in the eCRF.

It is recognised that some patients with advanced melanoma can have a transient tumour flare in the first few months after start of immunotherapy with subsequent disease response and this may be borne in mind when considering any early progression on study. The decision will be based on clinical judgment but to continue treatment on study after disease progression is identified by a scan, the patient should have:

- Absence of clinical symptoms and signs indicating disease progression (including worsening of laboratory values)
- No decline in performance status
- Absence of disease symptoms indicative of requiring alternative treatment
- No clinically relevant adverse effects related to study treatment

Patients in Cohort B of the study who have progression on study with IMM-101 + nivolumab treatment have the option to change on study to treatment with IMM-101 + ipilimumab, at the Investigator's discretion (see Section 7.5).

Any patients who discontinue study treatment for reasons other than progression and for whom no further treatment is deemed appropriate or desired, should remain on study and have scheduled scans until documented progression.

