# 8.5.3.10 Confirmatory Scans (RECIST 1.1 and irRC)

Confirmation of response (CR and PR) is required for RECIST 1.1 with the confirmatory scan being carried out at least 4 weeks after the scan from which a response was seen. Patients will then return to regular scheduled imaging every 8 weeks relative to the Week 12 scan (Cohort A) or Week 6 scan (Cohort B) and 12 weekly for patients still on study after Week 52. Patients who obtain a confirmation scan do not need to undergo scheduled imaging assessment 4 weeks later (e.g., if a patient obtains a scan at Week 16 to confirm a Week 12 response, their next scheduled scan would not be performed until Week 28, with no scan at Week 20).

Once a response is confirmed, repeat scans are not required to confirm subsequent instances of the same response.

Confirmatory scans for responses by irRC may be carried out at the discretion of the Investigator to assist in managing treatment on study.

If imaging shows PD, it is at the discretion of the Investigator whether to keep a patient on study treatment or to stop study treatment until imaging is repeated approximately 4 weeks later in order to confirm PD, per irRC recommendations.

If repeat scans confirm PD, then progression should be declared using the date of the initial scan. If repeat scans do not confirm PD, then the subject is considered not to have progressive disease per irRC.

If a confirmatory assessment is non-evaluable but the subsequent scan maintains the same response/progression, the response/progression can be considered confirmed (eg PR-NE-PR).

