5.13 EFFICACY EVALUATION

5.13.1 Primary Endpoint

The primary endpoint will be analysed using the ITT set and repeated for the PPS for Cohort A only.

Primary Analysis

The primary efficacy endpoint of the study is the ORR calculated from the BOR of subjects as assessed by RECIST 1.1.

The investigator response will be entered into the Response Assessment (RECIST 1.1) page of the electronic Case Report Form (eCRF) at each scan assessment to be used in the derivation of BOR.

A confirmed response will be used in the derivation of BOR. A confirmed response is defined as a response obtained from a scan repeated at least 4 weeks following a scan with designation of complete response (CR) or partial response (PR), as defined using Table 3 of RECIST 1.1. In addition, the following approaches will be taken:

- Where a confirmatory assessment is non-evaluable (NE) but the subsequent scan maintains the same response/progression, the response/progression will be considered confirmed (e.g. PR-NE-PR).
- Subjects without a confirmed response of CR or PR will have their next best response (stable disease (SD) or otherwise progressive disease (PD)) assigned as their BOR.
- Subjects without a BOR assessment, such as those with no post-baseline responses or only NE responses, will be assumed to have a BOR of PD using a worst-case approach.

For Cohort A, BOR is defined as the best confirmed response designation, recorded from the first post-baseline scan until and including the last scan on study for each subject.

For Cohort B, BOR is defined as the best confirmed response designation, recorded from the first post-baseline scan until and including the last scan on study for each subject for those receiving IMM-101 and nivolumab, or the last scan performed prior to treatment with ipilimumab. No scan performed once ipilimumab treatment commences will be included.

All scans within these periods, whether scheduled or unscheduled, will be evaluated for overall response.

ORR is calculated as the number of subjects with a BOR of confirmed CR or PR divided by the number of subjects in the analysis set. ORR is calculated for each cohort separately.

Summaries of BOR (best confirmed overall response designation)

The BOR will be summarised for each cohort. The ORR and accompanying exact binomial 95% confidence intervals (CI) will also be presented.

Listings of lesions assessments and BOR

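### The next scheduled scan is waived once a confirmation scan has been done, not once the response is confirmed, so an inevaluable or SD result can leave 12 weeks, or the rest of the study, with no required scan

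*Protocol*

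**What the plan says.** Four protocol texts give the waiver: 5.3, 8.5.1, 8.5.3.10 and Appendix 1 note 5. The wording in 8.5.1 is "Patients who obtain a confirmation scan do not need to undergo scheduled imaging assessment 4 weeks later". For a Week 12 response rescanned at Week 16, the same section adds that "their next scheduled scan would not be performed until Week 28, with no scan at Week 20".

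Section 8.5.1 foresees a failed confirmation. It says the original values must stay in the eCRF "even if the confirmatory scan does not confirm the results of the original scan". It gives no separate imaging rule for that case.

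Three other rules bear on the point:

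- **Inevaluable confirmation scan.** Protocol 8.5.3.10: "If a confirmatory assessment is non-evaluable but the subsequent scan maintains the same response/progression, the response/progression can be considered confirmed". SAP 5.13.1 applies the same PR-NE-PR rule when deriving BOR.
- **No confirmation.** SAP 5.13.1: "Subjects without a confirmed response of CR or PR will have their next best response", meaning SD, or otherwise PD.
- **End of study scan.** Protocol 8.3 requires one only if progression is not already documented and more than 8 weeks have passed since the last scan, or more than 12 weeks if that scan was after Week 52.

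**The concern.** Skipping a scan makes sense once a response is confirmed. It makes less sense when the repeat scan was inevaluable or showed SD, because the response is then still open and the next scan decides it. As written, both kinds of patient get the same waiver.

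Two results are exposed. The first is the confirmed ORR, the primary efficacy endpoint: a responder with an inevaluable repeat scan needs a further evaluable scan to count, and the waiver removes the nearest one. The second is PFS, because a progression in the unscanned interval is dated at the next scan. With 18 and 8 patients and an ORR meant to be compared with published data, one patient is visible in the result.

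**Working it through.** **Inputs.** Cohort A scans at Weeks 12, 20, ..., 76 and cohort B at Weeks 6, 14, ..., 78 (Appendix 1, 8-weekly). Confirmation is taken at 4 weeks after the response scan. Planned sizes are 18 and 8 (protocol 11.2). The interim ORR uses 11 and 5 patients (SAP 4). The end of study visit is Week 80 (protocol 8.3).

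**1. The plan's own example.** Response Week 12, repeat Week 16, Week 20 skipped, next scan Week 28. Gap = 28 − 16 = 12 weeks, as the protocol states. Without the waiver it is 20 − 16 = 4 weeks. With the ±7-day windows the gap runs from (28 − 1) − (13 + 4) = 10 to (28 + 1) − (11 + 4) = 14 weeks. For a Week 44 response rescanned at Week 48 with Week 52 waived, it is 60 − 48 = 12 weeks, or 64 − 48 = 16 if 12-weekly scanning then begins.

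**2. Where PR-NE-PR can fail.** Each row assumes an inevaluable repeat scan and no optional scan.

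| Setting | PR | NE | Waived | Next required scan |
|---|---|---|---|---|
| Final, cohort A, early | 12 | 16 | 20 | 28: confirmed if still PR, lost if not |
| Final, cohort A, late | 68 | 72 | 76 | None: 80 − 72 = 8 weeks, within the 12-week limit |
| Final, cohort B, late | 70 | 74 | 78 | None: 80 − 74 = 6 weeks, within the 12-week limit |
| Interim, cohort B | 14 | 18 | 22 | 30, which SAP 4.2 excludes |

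In the last three rows the response goes unconfirmed even if it never fades. A similar case arises at the cohort A interim: PR Week 44, NE Week 48, Week 52 waived (nominally day 52 × 7 = 364, just inside 12 months), next scan Week 60.

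**3. Weight of one patient (exact 95% CI; the responder counts are illustrative).**

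- Cohort A: 1/18 = 5.6 points. 8/18 = 44.4% (21.5 to 69.2) against 7/18 = 38.9% (17.3 to 64.3).
- Cohort B: 1/8 = 12.5 points. 2/8 = 25.0% (3.2 to 65.1) against 1/8 = 12.5% (0.3 to 52.7).
- At the interims: 1/11 = 9.1 points and 1/5 = 20 points.

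**4. PFS.** After an SD or inevaluable Week 16 scan, a progression arising in Weeks 16 to 20 is dated Week 28 instead of Week 20. That is 8 weeks, or 56/30.4375 = 1.84 months. A progression arising in Weeks 20 to 28 is dated Week 28 either way.

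**5. How likely.** The documents give no rate. For illustration in cohort A, take the 44% response rate the protocol cites for nivolumab. Assume that 5 to 20% of confirmation scans are inevaluable or do not confirm, and that 5 to 20% of those patients would be in PR at Week 20 but not at Week 28. Both ranges are assumptions.

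- Expected misclassified patients: 18 × 0.44 × 0.05 × 0.05 = 0.02, up to 18 × 0.44 × 0.20 × 0.20 = 0.32.
- Chance of at least one: 1 − (1 − 0.0011)^18 = 2%, up to 1 − (1 − 0.0176)^18 = 27%.

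This covers the early route only, not the late-response or interim routes.

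**The case against.** A reader might infer that the waiver also leaves a patient unscanned when the confirmation scan shows PD. The documents do not support that. Sections 5.3 and 8.5.3.10 have their own provision for PD, under which the investigator may keep the patient on treatment or choose "to stop study treatment until imaging is repeated approximately 4 weeks later in order to confirm PD, per irRC recommendations". The waiver removes only a scheduled scan, so the two can coexist. RECIST PFS would in any case already be dated at the scan showing PD.

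Several other points narrow the problem, and they stand:

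- If no repeat imaging was done at all, the patient has not had a confirmation scan and the Week 20 scan remains due. The issue is confined to scans done but not fully measured, or showing SD. Section 8.5.3.9 also lets a partly measured scan count where the missing lesions would not change the response.
- The PR-NE-PR rule has no upper time limit, so a PR still present at Week 28 confirms the response. After SD at Week 16, a PR at Week 28 can itself be confirmed later.
- The waiver is permissive, and unscheduled scans are allowed if clinically indicated and count toward BOR.
- In 5.3, a sentence about confirmed responses precedes the return to schedule, which suggests that the authors had confirmed responders in mind.
- A sensitivity analysis counts unconfirmed responses, as do duration of response, time to response, the subgroup tables and the irRC ORR. The study is descriptive.
- Confirmed responders have the same 12-week gap, and 12-week intervals are accepted after Week 52.
- A Study Operations Manual, which I have not seen, may add detail.

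These points limit the frequency and the consequences, but they do not supply the missing condition. Nothing in the protocol or SAP requires an early rescan after an inevaluable or SD confirmation scan, so ascertainment of the primary endpoint rests on site discretion. The sensitivity analysis shows the difference but does not repair the confirmed ORR or the PFS date. For confirmed responders the gap cannot undo the confirmation.

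**Conclusion.** The point holds in a limited form. The waiver is tied to having a confirmation scan, and followed as written it can score a true responder as SD in the confirmed ORR. At the final analysis this needs an inevaluable repeat scan plus either a response gone by the next required scan or a response too late in the schedule. At the cohort B interim it can happen to a patient whose response continues throughout. One patient is worth 5.6 points in cohort A or 12.5 in cohort B. The PFS effect is at most 8 weeks nominally, and only for progression arising in the first 4 weeks of the gap with no optional scan.

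It would be too strong to read this as a material bias in ORR, or as a claim that every patient with an unconfirmed response goes 12 weeks without imaging. The 12 weeks is the minimum the schedule requires, and the illustrative chance of a misclassification by the early cohort A route is 2 to 27% under assumed rates. This is a worthwhile low-cost correction, not a threat to the study.

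**What to change.** In protocol 5.3, 8.5.1, 8.5.3.10 and Appendix 1 note 5, make the waiver conditional, for example: *The scheduled scan 4 weeks after a confirmation scan may be omitted only if the confirmation scan is evaluable, was done at least 4 weeks after the first, and confirms the CR or PR; otherwise the scheduled scan is done.*

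A patient with an inevaluable or SD scan at Week 16 would then be scanned at Week 20. In cohort B, a Week 6 response rescanned at Week 10 without confirmation would be scanned at Week 14 instead of Week 22. Late responses would regain Week 76 or Week 78, and the cohort B interim would regain Week 22.

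The cost is one sentence in four places. No scan is added beyond the existing 8-weekly schedule; one already-scheduled scan is kept for the few patients whose response is not confirmed. Confirmed responders keep their waiver, and the SAP derivation of BOR needs no change.
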